### Additional analyses

To show the magnitude of the improvement of OI score of COMPASS-31, OI scores at baseline ( $OI_{\text{baseline}}$ ) and at W25 ( $OI_{W25}$ ), the proportion of subjects within the following categories will be analyzed. This analysis will show the proportion of the subjects with OI symptom score improvement at the end of the treatment period.

- $OI \text{ Score} \geq 36$
- $33 \geq OI \text{ Score} < 36$
- $30 \geq OI \text{ Score} < 33$
- $27 \geq OI \text{ Score} < 30$
- $24 \geq OI \text{ Score} < 27$
- $21 \geq OI \text{ Score} < 24$
- $18 \geq OI \text{ Score} < 21$
- $15 \geq OI \text{ Score} < 18$
- $12 \geq OI \text{ Score} < 15$
- $OI \text{ Score} < 12$

To show the magnitude of the improvement of TS score of COMPASS-31, TS scores at baseline ( $TS_{\text{baseline}}$ ) and at W25 ( $TS_{W25}$ ), the proportion of subjects within the following categories will be analyzed. This analysis will show the proportion of the subjects with TS symptom score improvement at the end of the treatment period.

- $\text{Total Score} \geq 91$
- $86 \geq \text{Total Score} < 91$
- $81 \geq \text{Total Score} < 86$
- $76 \geq \text{Total Score} < 81$
- $71 \geq \text{Total Score} < 76$
- $66 \geq \text{Total Score} < 71$

- $61 \geq \text{Total Score} < 66$
- $56 \geq \text{Total Score} < 61$
- $50 \geq \text{Total Score} < 56$
- $\text{Total Score} < 50$

To show the proportion of subjects with normal HR after 24 weeks of treatment also had improvement in their OI and TS of COMPASS-31, the correlation between HR and OI as well as TS will be done using the Spearman correlation. Sensitivity Analysis of Key Secondary Endpoints

The following sensitivity analyses are planned for the key secondary efficacy endpoints:

- using the PP analysis set
- using a tipping point analysis: for subjects with an ICE the HR and COMPASS-31 after the ICE (see Section 9.4.2.1.1 for further details) will be imputed using a multiple imputation (see Section 9.4.4).

#### 9.4.3. Multiplicity

Issues related to multiplicity arising from testing the primary endpoint and key secondary endpoints will be addressed using pre-defined hierarchical testing procedure of the primary and key secondary endpoints with following order at an alpha level of 2.5%:

1. Hypothesis tested: primary endpoint
2. Hypothesis tested: 1st key secondary endpoint; change from baseline in OI domain of the COMPASS-31
3. Hypothesis tested: 1st key secondary endpoint; change from baseline in COMPASS-31 total score
4. Hypothesis tested: 2nd key secondary endpoint; change from baseline in HR increase

#### 9.4.4. Multiple Imputation

For subjects with an ICE (see Section 9.4.2.1.1) that considers multiple imputation data after the ICE will be disregarded (if applicable) and be imputed using a multiple imputations approach.

**Intermittent missing replacement step:** If intermittent values are missing for any of the data included in the multiple imputation analysis, the intermittent values will be imputed first using a Markov Chain Monte Carlo method 50 times to create 50 data sets with only monotone missing. The corresponding data sets will be used as input data sets for replacement of the post-ICE missing values using monotone regression; as the preceding step led already to 50 data sets, the number of imputations in this step is to be set to 1.

**Imputation step:** Replacement of missing values for HRW5,0min, HRW5,10min, HRW9,0min, HRW9,10min, HRW13,0min, HRW13,10min, HRW17,0min, HRW17,10min, HRW21,0min, HRW21,10min, HRW25,0min, and HRW25,10min, OIW5, OIW9, and OIW25 as well as TSW5, TSW9, and TSW25 (if

applicable), will be done using multiple imputations based on monotone regression with the covariates treatment, country, HR at baseline, COMPASS-31 TS and OI at baseline and HR and COMPASS-31 TS and OI values from previous weeks by SAS® PROC MI for 50 imputations with a seed of 7562032. The HR value at the end of the standing test will be considered as the average of the two highest values within 10 minutes after start of the standing test.

**Analysis step:** For each of the 50 analyses of the primary and key secondary endpoints will be performed as outlined in Section 9.4.2.1 and Section 9.4.2.2.

For the primary endpoint, each subject's response status will be derived as in Section 9.4.2.1.

For the first key secondary endpoint, the imputed HR will be used.

For the second and third key secondary endpoints, the imputed COMPASS-31 values will be used.

**Combination step:** The corresponding results across the data sets are combined for overall inference using SAS® PROC MIANALYZE according to Rubin's rule to give the 1-sided p-values for hypothesis testing, and the corresponding measures (responder rate, mean, 95% CIs, as applicable).

#### 9.4.5. Tipping Point Analysis

A tipping point analysis will be done to assess the robustness of the assumptions for the multiple imputation and will be done only if primary analysis has a p-value < 0.025 (1-sided).

For each of the primary and key secondary endpoints, the treatment differences (D) are obtained from the main analysis as  $HR_{IgPro20, W25, 0min} - HR_{placebo, W25, 0min}$  and  $HR_{IgPro20, W25, 10min} - HR_{placebo, W25, 10min}$  (for primary and third key secondary endpoint) and  $OI_{IgPro20, W25} - OI_{placebo, W25}$  as well as  $TS_{IgPro20, W25} - TS_{placebo, W25}$  (for the first and second key secondary endpoints) from the primary analyses. The HR value at the end of the standing test will be considered as the average of the two highest values within 10 minutes after start of the standing test.

For each  $\lambda = 0.05$  to 1 (by 0.05) steps, subtract  $\lambda \times \Delta$  from the imputed values of the IgPro20 treatment group in each of the 50 imputed datasets from the primary analysis. Continue with the analysis and combination step as described above for each  $\lambda$ .

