### 9.2. Sample Size Determination

Based on the rationale presented in Section 4.3, assuming the proportion of subjects no longer meeting diagnostic criteria of post-COVID POTS as measured by standardized standing test at the end of the Double-blind Treatment Period. Sample size assumptions are based on the 30% and 60% response for the placebo and IgPro20 group, respectively; under

these assumptions, at least 126 subjects will be required to provide 90% power (2:1 randomization) to detect a 30% difference in proportion of responders using a Farrington-Manning test for a 1-sided alpha of 2.5%. An additional 18 subjects will be randomized to account for a futility analysis at 54 subjects, and an additional 33 subjects will be randomized to ensure > 100 subjects treated with IgPro20 for >1 year will be achieved considering approximately 20% early drop out. Therefore, the final number of patients to be randomized is 177 (118:59).

For hypothesis testing, an alpha of 2.5% (1-sided) will be used. Randomization will be continued if the dropout rate is over 10%.

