#### 9.4.2.1.2. Sensitivity Analysis

The following sensitivity analyses are planned for the primary efficacy endpoint:

- Using the PP analysis set.
- Using a tipping point analysis: for subjects with an ICE (see Section 9.4.2.1.1 for further details), the HR after the ICE will be imputed using a multiple imputations approach (see Section 9.4.4 for further details).

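### The tipping-point shift in Protocol 9.4.5 ends at lambda = 1, about placebo level for IgPro20 subjects imputed under randomized treatment, so finding no tipping point cannot distinguish real robustness from a grid that stopped early

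*Protocol*

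**What the plan says.** Protocol 9.4.5 gives the purpose: "A tipping point analysis will be done to assess the robustness of the assumptions for the multiple imputation". It is run only after a significant primary result (one-sided p below 0.025). The Week 25 difference, IgPro20 minus placebo, is taken from the main analysis. Lambda then goes from 0.05 "to 1 (by 0.05) steps, subtract" lambda times that difference "from the imputed values of the IgPro20 treatment group in each of the 50 imputed datasets from the primary analysis". The analysis and combination steps are repeated for each lambda. The section contains no lambda above 1, no shift of the placebo arm, no worst case, and no instruction to continue until significance is lost.

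Section 9.4.2.1.2 lists this as a sensitivity analysis of the primary endpoint: "Using a tipping point analysis: for subjects with an ICE". Protocol Table 5 sets the starting imputation:

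- **Other treatment discontinuations and loss to follow-up:** multiple imputation under randomized treatment, for all endpoints.
- **Discontinuation for lack of efficacy, related adverse event or non-compliance, and prohibited therapies:** non-responder for the primary; imputation from the placebo group for the key secondaries.
- **Death unrelated to product or disease:** imputation from the placebo group, for all endpoints.

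SAP 2.0, Sections 5, 10.6 and 10.7, cancels the imputation and marks the tipping-point analysis not applicable after early termination.

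**The concern.** A tipping-point analysis should show how unfavourable the missing outcomes must be before the conclusion changes. For subjects imputed under randomized treatment, this grid only moves from the imputed effect (lambda near 0) to no effect (lambda = 1).

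The protocol itself treats worse outcomes as possible. Table 5 counts a subject who stops for lack of efficacy or a related adverse event as a non-responder, a 0% response against the assumed 30% on placebo. If some subjects recorded as lost to follow-up or as stopping for other reasons in fact left for those causes, the protocol's own rule would put them below anything the grid tests. At stake is the meaning of a statement that no tipping point was found.

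**Working it through.** **Inputs.** Protocol 9.2: "Sample size assumptions are based on the 30% and 60% response for the placebo and IgPro20 group, respectively"; "For hypothesis testing, an alpha of 2.5% (1-sided) will be used"; 118:59 randomized. SAP Appendix 1 also uses a 55% active rate in its futility scenarios. The imputed share f is an assumption, 10% to 30%, equal in both arms. The roughly 20% early drop-out in 9.2 concerns securing one-year exposure, not missing Week 25 outcomes.

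**The plan's own figure.** Farrington-Manning at zero margin is the pooled-variance test. Placebo n = [1.960·√(0.5·0.5·1.5) + 1.282·√(0.3·0.7 + 0.6·0.4/2)]² / 0.30² = 41.7, so 42, plus 84 on IgPro20 = 126, as stated. Power at 177 is 97.3%.

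**Expected result at the end of the grid and in the worst case.** At lambda = 1 the IgPro20 rate is p_T(1−f) + p_C·f. With all imputed IgPro20 subjects as non-responders it is p_T(1−f). Then z = difference / √[p̄(1−p̄)(1/118 + 1/59)].

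| IgPro20 vs placebo | f | Rate at lambda = 1 | z | Worst-case rate | z |
|---|---|---|---|---|---|
| 60% vs 30% | 10% | 57% | 3.39 | 54% | 3.02 |
| 60% vs 30% | 20% | 54% | 3.02 | 48% | 2.29 |
| 60% vs 30% | 30% | 51% | 2.65 | 42% | 1.55 |
| 55% vs 30% | 10% | 52.5% | 2.84 | 49.5% | 2.47 |
| 55% vs 30% | 20% | 50% | 2.53 | 44% | 1.80 |
| 50% vs 30% | 20% | 46% | 2.04 | 40% | 1.30 |

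**Adding Rubin variance (f = 20%).** These z values treat imputed outcomes as observed, whereas Protocol 9.4.4 combines by Rubin's rule. Ignoring covariates, the between-imputation variance per arm is about f²[q(1−q)/(f·n) + φ²/((1−f)n)], where q = 0.30 is the imputed response rate and φ = 0.348 is the normal density at that quantile. This gives 0.00041 on IgPro20 and 0.00081 on placebo, 0.00122 together. Total variance is W + 1.02·B for 50 imputations.

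- 55% vs 30%, lambda = 1: 0.20/√(0.00624 + 0.00125) = 2.31, still significant.
- 50% vs 30%, lambda = 1: 0.16/√(0.00613 + 0.00125) = 1.86, no longer significant.
- 60% vs 30%, worst case (placebo arm imputed only): 0.18/√(0.00619 + 0.00083) = 2.15, still significant.

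**Simulation.** 600 trials per scenario, 118:59, 50 imputations, Rubin's rules. The model is a normal heart-rate increase calibrated to 60% vs 30%, covariate correlation 0.5, all imputation under randomized treatment, heart-rate criterion only. Shares of significant trials:

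| f | Tips by lambda = 1 | Tips if all imputed IgPro20 fail | Hidden by the cap | Never tips |
|---|---|---|---|---|
| 10% | 4.0% | 10.6% | 6.6% | 89.4% |
| 20% | 11.1% | 38.2% | 27.1% | 61.8% |
| 30% | 27.2% | 72.1% | 44.9% | 27.9% |

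Among borderline results (one-sided p from 0.005 to 0.025; 49, 69 and 100 trials), 47%, 86% and 99% tip by lambda = 1 at f = 10%, 20% and 30%.

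**The case against.** Several stronger readings are tempting, and the documents do not support them.

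- **A reader might infer that the cap is the main reason no tipping point is found.** At 60% vs 30% with 20% imputed, 89% of significant trials do not tip by lambda = 1. About 62 of those 89 points do not tip under any outcome for the imputed IgPro20 subjects, so an extended grid would report the same.
- **A reader might infer that no imputed IgPro20 subject is ever tested below placebo.** Section 9.4.5 shifts all imputed IgPro20 values without exception. Events imputed from the placebo group are therefore moved beyond placebo. That covers several events for the key secondaries, but only unrelated death for the primary.
- **A reader might take 50% vs 30% as a missed tipping point.** At 20% imputed, once Rubin variance is included, it tips inside the grid.

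It is also fair to say that Table 5 already makes the discontinuations most likely to do badly non-responders for the primary. The imputed share may then be below 20%, and at 10% even the 55% example has no tipping point (worst-case z 2.47). Removing the whole effect is a coherent stress test, and borderline results often tip within it.

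These arguments limit the size of the problem. They do not answer the narrower point: when nothing tips by lambda = 1, the planned output cannot say whether anything would tip further out.

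**Conclusion.** The point holds as a minor weakness of the protocol's planned sensitivity analysis. For IgPro20 subjects imputed under randomized treatment the grid ends at about placebo level and cannot separate robustness from an early stop. At 60% vs 30% the expected worst case stays significant at 10% and 20% imputed (z 3.0 and 2.3) and is lost at 30% (z 1.55). At 55% vs 30% with 20% imputed, the expected result survives the whole grid but not the worst case.

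Across simulated significant trials at the design rates, the cap hides a tipping point in about 7%, 27% and 45% at 10%, 20% and 30% imputed. These figures rest on the assumed imputed share, equal in both arms, and on the simulation model. No result is affected: the study stopped with 16 of 177 randomized and SAP 2.0 does not run the analysis.

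**What to change.** In Protocol 9.4.5, and in any reuse of this design:

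1. Keep increasing lambda beyond 1 until the one-sided p-value reaches 0.025 or, for the primary endpoint, all imputed IgPro20 subjects are non-responders.
2. Report the shift at which the result tips and the imputed IgPro20 response rate it implies, or state that no tipping point exists.
3. State how events already imputed from the placebo group are shifted.
4. Use one symbol for the treatment difference; the section writes both D and Δ.

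The cost is a few more iterations of the same code and possibly a less favourable robustness statement. Nothing changes for the 16 randomized subjects.

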#### 9.4.6. Exploratory Analysis

The proportion of subjects with orthostatic hypotension, the change in Malmö Symptom score, EQ-5D-5L utility scores and visual analog scale, WPAI total and domain scores, SF-12 domain score, the remaining domains of COMPASS-31 and the proportion of patients who achieved the clinically meaningful improvement in OI and total domains of COMPASS-31 at the end of the Double-blind Treatment Period for IgPro20 vs placebo will be summarized.

#### 9.4.7. Safety Analyses

All safety analyses will be performed by treatment group using the Safety Analysis Set. Adverse events will be coded using the Medical Dictionary for Regulatory Activities.

Treatment-emergent AEs (TEAEs) are defined as AEs reported at or after the start of IMP administration. The number and percentage of subjects with TEAEs will be reported. Frequency counts and percentages will also be presented for subjects with treatment-emergent SAEs, TEAEs leading to withdrawal or discontinuation of investigational product, TEAEs by severity, and TEAEs by relationship to investigational product. All AEs will be listed.

Analyses of other safety assessments such as ECGs, vital signs, and clinical laboratory safety markers will be described in the SAP.

#### **9.4.8. Pharmacokinetics Analyses**

IgG concentrations will be listed for individual subjects and summarized by nominal (planned) visit and timepoints, as well as by treatment group (IgPro20 vs placebo). Individual concentration-time profiles and mean ( $\pm$  SD) profiles will be plotted using actual time points for individual plots and nominal (planned) time points for mean profiles on both log-linear and linear scales.

$C_{\text{troughs}}$  will be measured for all subjects. Other parameters, including  $AUC_{0-\text{tau}}$  ( $\text{tau}=\text{Day } 7$ ),  $C_{\text{max}}$  and  $T_{\text{max}}$ , will be derived for the subjects with serial sampling on Week 41 using noncompartmental methods. The PK parameters will be listed individually and summarized.

Additional information on the analyses of PK parameters will be provided in the SAP. The PK Analysis Set or PK Substudy Analysis Set will be used.

The IgG concentration data may be used, possibly in combination with IgPro20 data from previous studies, to further develop the population PK model.

#### **9.4.9. Pharmacodynamic and Biomarker Analyses**

If applicable, additional exploratory biomarker analyses will be described in a separate biomarker SAP and may be reported outside of the SAP and clinical study report.

#### **9.4.10. Pharmacokinetic / Pharmacodynamic Analyses**

Relationships between trough concentrations and other PD/biomarker endpoints may be explored through graphical and statistical regression analyses as appropriate. Details will be provided in the SAP.

#### **9.4.11. Other Analyses**

##### **Subgroup Analyses of Primary Endpoint**

Internal consistency of observed treatment effect across major subgroups on the primary endpoint will be investigated. Subgroup factors are shown in the list below:

- Subjects received a COVID-19 vaccine
  - Yes
  - No

- Age
  - $\geq 18 - < 20$  Years
  - $\geq 20 - < 26$  Years
  - $\geq 26 - < 46$  Years
  - $\geq 46 - < 65$  Years
  - $\geq 65$  Years
- Sex:
  - Female
  - Male
- Baseline total COMPASS-31 score:
  - $\geq 40 - < 46$
  - $\geq 46 - < 51$
  - $\geq 51 - < 56$
  - $\geq 56$

Subgroup analysis will use the same analytical approach as in the primary endpoint analysis.

#### **9.4.12. Interim Analysis**

Simulation within EAST software was used to determine time point and operating characteristics of an interim analysis for futility using a gamma family alpha spending function. There is neither a plan for sample size re-estimation during the trial nor for early stopping for efficacy. For a futility boundary of 10% (ie, if response rate with IgPro20 – response rate with placebo is  $< 10\%$ ) there is a probability to stop under H0 (no treatment effect) of 75.8% and to stop the study under H1 (assumed treatment effect of 30%) of 7.4% at the time the futility analysis is performed (when 54 subjects have completed the first 24 weeks of treatment). Please see below for further scenarios (total N of 177). This boundary and timepoint for the interim analysis was considered suitable considering recruitment.

The detailed of boundaries and timepoint for the interim analysis will be described in IDMC SAP and IDMC charter.

## **10. SUPPORTING DOCUMENTATION AND OPERATIONAL CONSIDERATIONS**

### **10.1. Regulatory, Ethical, and Study Oversight Considerations**

#### **10.1.1. Clinical Trial Research Agreement**

This study will be conducted under a Clinical Trial Research Agreement between the Sponsor and the institution(s) representing the investigational study site(s). Financial support to the investigational site(s) will be detailed in the Clinical Trial Research Agreement. The Clinical Trial Research Agreement must be signed before the commencement of the study and will clearly delineate the responsibilities and obligations of investigator and Sponsor and will form the contractual basis under which the clinical study will be conducted. Clinical Trial Research Agreements may be executed by electronic signature in compliance with 21 CFR Part 11 and simple or advanced electronic signature according to EU Regulation No 910/2014 - eIDAS.

#### **10.1.2. Regulatory and Ethics Considerations**

This study will be conducted in accordance with the Clinical Study Protocol (CSP) and with the following:

Consensus ethical principles derived from international guidelines including the Declaration of Helsinki.

- Applicable ICH GCP Guidelines.
- Applicable laws and regulations.
- The CSP, CSP amendments, Informed Consent Form (ICF), Investigator's Brochure, and other relevant documents (eg, advertisements) must be submitted to an Institutional Review Board (IRB) / Independent Ethics Committee (IEC) by the investigator and reviewed and approved by the IRB / IEC before the study is initiated.
- Any CSP amendments will require IRB / IEC approval before implementation of changes made to the study design, except for changes necessary to eliminate an immediate hazard to study subjects.
- CSP and CSP amendments will require health authority approval prior to initiation except for changes necessary to eliminate an immediate hazard to study subjects.

The investigator will be responsible for the following:

- Providing written summaries of the status of the study to the IRB / IEC annually or more frequently in accordance with the requirements, policies, and procedures established by the IRB / IEC.
- Notifying the IRB / IEC of SAEs or other significant safety findings as required by IRB / IEC procedures.

- Providing oversight of the conduct of the study at the site and adherence to requirements of 21 CFR, ICH guidelines, the IRB / IEC, European Clinical Trials Regulation 536/2014 for clinical studies (if applicable), European Medical Device Regulation 2017/745 for clinical device research (if applicable), and all other applicable local regulations.

### **10.1.3. Informed Consent Process**

Informed consent will be obtained from all subjects or legally authorized representatives, if appropriate, before any study-related procedures are performed.

The investigator or delegate will explain the nature of the study to the subject or their legally authorized representative and answer all questions regarding the study.

Subjects or their legally authorized representative must be informed that their participation is voluntary. Subjects or their legally authorized representative will be required to sign a statement of informed consent, either via paper or electronic means, that meets the applicable requirements of 21 CFR 50, local regulations, ICH guidelines, Health Insurance Portability and Accountability Act requirements, and the IRB / IEC or study site.

The medical record must include a statement that written informed consent was obtained before the subject was enrolled in the study and the date the written consent was obtained. The authorized person obtaining the informed consent must also sign the ICF.

Subjects or their legally authorized representative must be reconsented to the most current version of the ICF(s) during their participation in the study.

A copy of the ICF(s) must be provided to the subject or their legally authorized representative.

OR

The ICF will contain a separate section or addendum that addresses the use of samples for optional exploratory research. The investigator or authorized delegate will explain to each subject the objectives of the exploratory research. Subjects will be told that they are free to refuse to participate and may withdraw their consent at any time and for any reason during the storage period.

